10.8. Appendix 8: Protocol Amendment History

Not applicable.

10.9. Appendix 9: Protocol Amendment History

The Protocol Amendment Summary of Changes Table for the current amendment is located directly before the Table of Contents (TOC).

Amendment (a): 03 March 2021

This amendment is considered to be nonsubstantial based on the criteria set forth in Article 10(a) of Directive 2001/20/EC of the European Parliament and the Council of the European Union.

Overall Rationale for the Amendment

To include clarification regarding how the percentage of the standardized meal to be consumed by each participant will be calculated.

Section # and Name	Description of Change	Brief Rationale
5 Study Population	Clinical laboratory assessments and vital signs may be repeated at the discretion of the investigator in order to confirm eligibility	per request from the PI
5.1 Inclusion Criteria	Bilateral salpingectomy added to inclusion #6	for consistency across the protocol
5.2 Exclusion Criteria	ECG exclusion now applicable at screening only instead of during 'baseline period'	for clarity
5.3.1 Meals and Dietary Restrictions	Text amended to outline: 
 • that components of the standardized meal will be weighed and documented in grams both pre- and post-meal to determine the percentage of the meal consumed by the participant. • that participants will complete the meal 30 minutes prior to dosing. 	for clarity
8.2.3 Electrocardiograms	ECGs will be interpreted by the investigator – not a qualified physician or qualified designee	for clarity

10.2 Appendix 2: Clinical Laboratory Tests	Partial thromboplastin time removed from list of coagulation parameters	vendor does not perform PTT assay; only aPTT
	Table footnote added to state that urinalysis will be performed by dipstick	for clarity
Appendix 4: Contraceptive Guidance and Collection of Pregnancy Information	Tubal ligation added to the category description of women not of childbearing potential	for consistency across the protocol
	Bilateral salpingectomy added to the category description of women not required to use contraception	for consistency across the protocol

11. References

Boehringer Ingelheim. Pradaxa® (dabigatran etexilate) prescribing information. July 2020; Accessed at <https://docs.boehringer-ingelheim.com/Prescribing%20Information/PIs/Pradaxa/Pradaxa.pdf> on 10 March 2020.

2. ABBREVIATIONS

Abbreviations pertain to the Statistical Analysis Plan (SAP) only (not the tables, figures and listings [TFLs]).

AE	Adverse event
ALP	Alkaline phosphatase
ALT	Alanine aminotransferase
AST	Aspartate aminotransferase
AUC	Area under the concentration versus time curve
AUC(0-∞)	Area under the concentration versus time curve from time zero to infinity
AUC(0-t _{last})	Area under the concentration versus time curve from time zero to time t, where t is the last time point with a measurable concentration
BQL	Below the quantifiable lower limit of the assay
CI	Confidence interval
CL/F	Apparent total body clearance of drug calculated after extra-vascular administration
C _{max}	Maximum observed drug concentration
CRU	Clinical Research Unit
CSR	Clinical Study Report
DDI	Drug-drug interaction
ECG	Electrocardiogram
ICH	International Conference on Harmonisation
MedDRA	Medical Dictionary for Regulatory Activities
P-gp	P-glycoprotein
PK	Pharmacokinetic
SAE	Serious adverse event
SAP	Statistical Analysis Plan
SD	Standard deviation
t _{1/2}	Half-life associated with the terminal rate constant (λ_z) in non-compartmental analysis
TBL	Total bilirubin
TEAE	Treatment-emergent adverse event
TFLs	Tables, Figures, and Listings
t _{max}	Time of maximum observed drug concentration

ULN	Upper limit of normal
V_{ss}/F	Apparent volume of distribution at steady state after extra-vascular administration
V_z/F	Apparent volume of distribution during the terminal phase after extra-vascular administration
WHO	World Health Organization

3. INTRODUCTION

This SAP has been developed after review of the Clinical Study Protocol (final version dated 21 December 2020).

This SAP describes the planned analysis of the safety, tolerability and pharmacokinetic (PK) data from this study. A detailed description of the planned TFLs to be presented in the clinical study report (CSR) is provided in the accompanying TFL shell document.

The intent of this document is to provide guidance for the statistical and PK analyses of data. In general, the analyses are based on information from the protocol, unless they have been modified by agreement with Eli Lilly and Company. A limited amount of information concerning this study (e.g., objectives, study design) is given to help the reader's interpretation. For open-label studies, this SAP must be signed off prior to first participant visit for this study. When the SAP and TFL shells are agreed upon and finalized, they will serve as the template for this study's CSR.

This SAP supersedes the statistical considerations identified in the protocol; where considerations are substantially different, they will be so identified. If additional analyses are required to supplement the planned analyses described in this SAP, they may be performed and will be identified in the CSR. Any substantial deviations from this SAP will be agreed upon with Eli Lilly and Company and identified in the CSR. Any minor deviations from the TFLs may not be documented in the CSR.

This SAP is written with consideration of the recommendations outlined in the International Conference on Harmonisation (ICH) E9 Guideline entitled Guidance for Industry: Statistical Principles for Clinical Trials¹ and the ICH E3 Guideline entitled Guidance for Industry: Structure and Content of Clinical Study Reports².

4. STUDY OBJECTIVES AND ENDPOINTS

Objectives	Endpoints
Primary	

To evaluate the effect of selpercatinib on P-glycoprotein (P-gp) activity in healthy participants.	
Maximum observed drug concentration (C_{max}) and area under the concentration versus time curve from time zero to infinity ($AUC[0-\infty]$) of dabigatran to assess P-gp activity.
Secondary	

To evaluate the safety and tolerability of dabigatran in combination with selpercatinib in healthy participants.To evaluate the PK of selpercatinib.	
Summary of the number of treatment-emergent adverse events (TEAEs) and serious adverse events (SAEs).C_{max}, $AUC(0-\infty)$, and time of maximum observed drug concentration (t_{max}) of selpercatinib.

5. STUDY DESIGN

This is a Phase 1, fixed-sequence, open-label study in healthy participants that will study dabigatran P-gp drug-drug interaction (DDI) with selpercatinib. The anticipated study duration for each individual participant is approximately 8 weeks.

Screening

All participants will be screened within 28 days prior to enrollment (Day 1).

Treatment and Assessment Period

Eligible participants will take part in 1 treatment period. Participants will be admitted to the clinical research unit (CRU) on Day -1 and remain resident in the CRU until discharge on Day 11. All participants will receive a single dose of 150 mg dabigatran on Day 1 and a single dose of 150 mg dabigatran coadministered with a single dose of 160 mg selpercatinib on Day 8. There will be a washout period of 7 days between dosing on Days 1 and 8.

PK blood sampling and safety assessments, including vital signs measurements, physical examinations, clinical laboratory tests, electrocardiograms (ECGs), and adverse event (AE) recording, will be performed.

Follow-up

Participants will return to the CRU for a safety follow-up visit within 14 to 17 days after the final dose.

The study schema is shown in [Figure 1](#).

[figure not shown]

Figure 1: J2G-MC-JZJV Study Schema

6. TREATMENTS

The following is a list of the study treatment abbreviations that will be used in the TFLs. In AE outputs, treatment labels will also contain "(Day X)" information.

Day	Study Treatment Name	Treatment order in TFL
1	150 mg dabigatran	1
8	150 mg dabigatran + 160 mg selpercatinib	2

7. SAMPLE SIZE JUSTIFICATION

Approximately [REDACTED] CCI will be enrolled so that approximately [REDACTED] CCI complete the study. To evaluate the effect of selpercatinib on P-gp activity, it is important that the ratio of geometric means is estimated with reasonable precision. [REDACTED] CCI

[REDACTED]

[REDACTED]

8. DEFINITION OF ANALYSIS POPULATIONS

The “Entered” population will consist of all participants who signed the informed consent form.

The “Enrolled/Intent-to-Treat” population will consist of all participants assigned to treatment, regardless of whether they take any doses of study intervention, or if they take the correct treatment.

The “Safety” population will consist of all participants assigned to dabigatran, and who take at least one dose of study intervention.

The “Pharmacokinetic Analysis” population will consist of all participants who received at least one dose of dabigatran and have evaluable PK data. Participants may be excluded from the PK summary statistics and statistical analysis if a participant has an AE of vomiting that occurs at or before 2 times median t_{max} , or 2 times individual t_{max} if individual t_{max} is achieved.

All protocol deviations that occur during the study will be considered for their severity/impact and will be taken into consideration when participants are assigned to analysis populations.

9. STATISTICAL METHODOLOGY

9.1 General

Data listings will be provided for all data that are databased. Summary statistics and statistical analysis will only be presented for data where detailed in this SAP. For continuous data, summary statistics will include the arithmetic mean, arithmetic standard deviation (SD), median, minimum, maximum and N; for log-normal data (e.g. the PK parameters: AUCs and C_{max}) the geometric mean and geometric coefficient of variation will also be presented. For categorical data, frequency count and percentages will be presented. Data listings will be provided for all participants up to the point of withdrawal, with any participants excluded from the relevant

population highlighted. Summary statistics and statistical analyses will generally only be performed for participants included in the relevant analysis population. For the calculation of summary statistics and statistical analysis, unrounded data will be used.

Mean change from baseline is the mean of all individual participants' change from baseline values. Each individual change from baseline will be calculated by subtracting the individual participant's baseline value from the value at the timepoint. The individual participant's change from baseline values will be used to calculate the mean change from baseline using a SAS procedure such as Proc Univariate.

Data analysis will be performed using SAS® Version 9.4 or greater.

9.2 Demographics and Participant Disposition

Participant disposition will be listed. The demographic variables age, sex, race, ethnicity, country of enrolment, site ID, body weight, height and body mass index will be summarized and listed. All other demographic variables will be listed only.

9.3 Pharmacokinetic Assessment

9.3.1 Pharmacokinetic Analysis

Noncompartmental methods applied with a validated software program (Phoenix WinNonlin Version 8.1 or later) to the plasma concentrations of dabigatran and selpercatinib will be used to determine the following PK parameters, when possible:

Parameter	Units	Definition
AUC(0-t _{last})	ng.h/mL	area under the concentration versus time curve from time zero to time t, where t is the last time point with a measurable concentration
AUC(0-∞)	ng.h/mL	area under the concentration versus time curve from time zero to infinity
C _{max}	ng/mL	maximum observed drug concentration
t _{max}	h	time of maximum observed drug concentration
t _{1/2}	h	half-life associated with the terminal rate constant (λ_z) in non-compartmental analysis
CL/F	L/h	apparent total body clearance of drug calculated after extra-vascular administration
V _{Z/F}	L	apparent volume of distribution during the terminal phase after extra-vascular administration
V _{ss/F}	L	apparent volume of distribution at steady state after extra-vascular administration

Additional PK parameters may be calculated, as appropriate.

The software and version used for the final analyses will be specified in the CSR. Any exceptions or special handling of data will be clearly documented within the CSR.

Formatting of tables, figures and abbreviations will follow the Eli Lilly Global PK/PD/TS Tool: NON-COMPARTMENTAL PHARMACOKINETIC STYLE GUIDE. The version of the tool effective at the time of PK analysis will be followed.

General PK Parameter Rules

- Actual sampling times will be used in the final analyses of individual PK parameters, except for non-bolus pre-dose sampling times which will be set to zero.
- The C_{max} and t_{max} will be reported from observed values. If C_{max} occurs at more than one timepoint, t_{max} will be assigned to the first occurrence of C_{max} .
- The AUC parameters will be calculated using a combination of the linear and logarithmic trapezoidal methods (linear-log trapezoidal rule). The linear trapezoidal method will be applied up to t_{max} and then the logarithmic trapezoidal method will be used after t_{max} . The minimum requirement for the calculation of AUC will be the inclusion of at least three consecutive plasma concentrations above the lower limit of quantification, with at least one of these concentrations following C_{max} .
- The $t_{1/2}$ will be calculated, when appropriate, based on the apparent terminal log-linear portion of the concentration-time curve. The start of the terminal elimination phase for each participant will be defined by visual inspection and generally will be the first point at which there is no systematic deviation from the log-linear decline in plasma concentrations. Half-life will only be calculated when a reliable estimate for this parameter can be obtained comprising of at least 3 data points. If $t_{1/2}$ is estimated over a time window of less than 2 half-lives, the values will be flagged in the data listings. Any $t_{1/2}$ value excluded from summary statistics will be documented in the footnote of the summary table.
- A uniform weighting scheme will be used in the regression analysis of the terminal log-linear portion of the concentration-time curve.
- The parameters based on predicted last quantifiable drug concentration will be reported.

Individual PK Parameter Rules

- Only quantifiable concentrations will be used to calculate PK parameters with the exception of special handling of certain concentrations reported below the lower limit of quantitation (BQL). Plasma concentrations reported as BQL will be set to a value of zero when all of the following conditions are met:
 - The compound is non-endogenous.
 - The samples are from the initial dose period for a participant or from a subsequent dose period following a suitable wash-out period.
 - The time points occur before the first quantifiable concentration.

- All other BQL concentrations that do not meet the above criteria will be set to missing.
- Also, where two or more consecutive concentrations are BQL towards the end of a profile, the profile will be deemed to have terminated and therefore any further quantifiable concentrations will be set to missing for the calculation of the PK parameters unless it is considered to be a true characteristic of the profile of the drug.

Individual Concentration vs. Time Profiles

- Individual concentrations will be plotted utilizing actual sampling times.
- The terminal point selections will be indicated on a semi-logarithmic plot.

Average Concentration vs. Time Profiles

- The average concentration profiles will be graphed using scheduled (nominal) sampling times.
- The average concentration profiles will be graphed using arithmetic average concentrations.
- The pre-dose average concentration for single-dose data from non-endogenous compounds will be set to zero. Otherwise, only quantifiable concentrations will be used to calculate average concentrations.
- Concentrations at a sampling time exceeding the sampling time window specified in the protocol, or $\pm 10\%$, will be excluded from the average concentration profiles.
- Concentrations excluded from the mean calculation will be documented in the CSR.
- A concentration average will be plotted for a given sampling time only if 2/3 of the individual data at the time point have quantifiable measurements that are within the sampling time window specified in the protocol or $\pm 10\%$. An average concentration estimated with less than 2/3 but more than 3 data points may be displayed on the mean concentration plot if determined to be appropriate and will be documented within the CSR.

Treatment of Outliers during Pharmacokinetic Analysis

Application of this procedure to all PK analyses is not a requirement. Rather, this procedure provides justification for exclusion of data when scientifically appropriate. This procedure describes the methodology for identifying an individual value as an outlier for potential exclusion, but does not require that the value be excluded from analysis. The following methodology will not be used to exclude complete profiles from analysis.

Data within an Individual Profile

A value within an individual profile may be excluded from analysis if any of the following criteria are met:

- For PK profiles during multiple dosing, the concentration of the pre-dose sample exceeds all measured concentrations for that individual in the subsequent post-dose samples.
- For PK profiles during single dosing of non-endogenous compounds, the concentration in a pre-dose sample is quantifiable.
- For any questionable datum that does not satisfy the above criteria, the profile will be evaluated and results reported with and without the suspected datum.

Data between Individual Profiles

1. If $n < 6$, then the dataset is too small to conduct a reliable range test. Data will be analyzed with and without the atypical value, and both sets of results will be reported.
2. If $n \geq 6$, then an objective outlier test will be used to compare the atypical value to other values included in that calculation:
 - a. Transform all values in the calculation to the logarithmic domain.
 - b. Find the most extreme value from the arithmetic mean of the log transformed values and exclude that value from the dataset.
 - c. Calculate the lower and upper bounds of the range defined by the arithmetic mean $\pm 3 \times \text{SD}$ of the remaining log-transformed values.
 - d. If the extreme value is within the range of arithmetic mean $\pm 3 \times \text{SD}$, then it is not an outlier and will be retained in the dataset.
 - e. If the extreme value is outside the range of arithmetic mean $\pm 3 \times \text{SD}$, then it is an outlier and will be excluded from analysis.

If the remaining dataset contains another atypical datum suspected to be an outlier and $n \geq 6$ following the exclusion, then repeat step 2 above. This evaluation may be repeated as many times as necessary, excluding only one suspected outlier in each iteration, until all data remaining in the dataset fall within the range of arithmetic mean $\pm 3 \times \text{SD}$ of the log-transformed values.

Reporting of Excluded Values

Individual values excluded as outliers will be documented in the CSR. Approval of the CSR will connote approval of the exclusion.

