Pharmacokinetic blood sampling and safety assessments, including vital signs measurements, physical examinations, clinical laboratory tests, ECGs, and AE recording, will be performed according to the SoA (Section 1.3).

Follow-up

Participants will return to the CRU for a safety follow-up visit within 14 to 17 days after the final dose.

Disclosure Statement: This is a Phase 1, fixed-sequence, open-label study in healthy participants.

Number of Participants:

Up to 40 participants will be enrolled to ensure that at least 30 evaluable participants complete.

Intervention Groups and Duration:

This is a single-group study, consisting of single oral doses of dabigatran (Day 1) and single oral doses of dabigatran and selpercatinib (Day 8).

Dabigatran/Selpercatinib	
Day 1	Day 8
Dabigatran (150 mg)	Dabigatran (150 mg) + Selpercatinib (160 mg)

A single oral dose of dabigatran etexilate 150 mg will be administered in the morning of Day 1. On the morning of Day 8, a single dose of dabigatran etexilate 150 mg and selpercatinib 160 mg will be administered orally with approximately 240 mL of room temperature water while in a sitting position. Participants will not be allowed to lie supine for 2 hours after dosing, unless clinically indicated or for study procedures.

During the confinement period, participants will consume only food and beverages that are provided to them by the CRU staff. Standard meals (e.g., breakfast, lunch, dinner, and snack) will be provided to the participants while resident at the CRU.

[figure not shown]
Dabigatran and selpercatinib will be administered with food using a standardized unit meal.

The macronutrient composition of the standardized meals for dabigatran and selpercatinib administration should be targeted to provide approximately 50% of the calories from carbohydrates, 15% protein, and 35% fat. The total calories for the standardized meal to be consumed with each dose is expected to be approximately 685 calories.

Participants will consume the standardized meal 30 minutes prior to administration of study intervention and participants should eat this meal in 30 minutes or less. No additional food should be allowed for at least 4 hours after drug administration.

Data Monitoring Committee: No

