4.2. Scientific Rationale for Study Design

A single 160-mg dose of selpercatinib was selected as it is the highest approved dose for selpercatinib use in adults.

In order to allow each participant to act as his/her own control for safety and PK comparisons, a fixed sequence design has been selected. This study will also be open-label as the study primary endpoint PK measures are objective rather than subjective.

Based on the $t_{1/2}$ of dabigatran, a period of 7 days between dabigatran doses is considered sufficient time for the study drug to washout.

Conducting the study in healthy participants mitigates the potential confounding effects of the disease state and concomitant medications in participants with metastatic RET fusion-positive NSCLC, advanced or metastatic RET-mutant MTC, or advanced or metastatic RET fusion-positive thyroid cancer. A population of healthy participants is frequently used in the assessment of the PK of both small and large molecules.

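### The SAP's leave-one-out 3-SD outlier test, whenever it is run, makes a valid value eligible for exclusion in about 19% of clean datasets of 30

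*SAP*

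**What the plan says.** The rule is in SAP 9.3.1, under the treatment of outliers, for data between individual profiles. With six or more values, "an objective outlier test will be used to compare the atypical value to other values included in that calculation". After log transformation, step 2b reads "Find the most extreme value from the arithmetic mean of the log transformed values and exclude that value from the dataset". Step 2c continues "Calculate the lower and upper bounds of the range defined by the arithmetic mean" plus or minus 3 SD of the values that remain. If the removed value lies outside that range, step 2e says "then it is an outlier and will be excluded from analysis". On iteration: "This evaluation may be repeated as many times as necessary, excluding only one suspected outlier in each iteration".

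The preamble to the same subsection is softer. It does not require the procedure for every PK analysis, offers it as a justification for exclusion where scientifically appropriate, does not oblige anyone to exclude a flagged value, and bars its use to remove complete profiles.

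For between-profile data, results with and without the atypical value are required only when there are fewer than six values. With six or more, excluded values are documented in the CSR.

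The design is paired. Protocol 4.2 states: "In order to allow each participant to act as his/her own control for safety and PK comparisons, a fixed sequence design has been selected".

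**The concern.** The test is called objective, but it is not calibrated. It takes the worst of n values and judges it against an SD computed without that value. A fixed multiplier of 3 allows for neither step, so clean data will often fail.

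The parameters at stake include dabigatran Cmax and AUC(0-∞), the primary endpoints of an open-label study. A test that often flags valid values is weak support for dropping one, particularly when use of the test is itself a judgement. The SAP also leaves open which values form the comparison set and what becomes of the participant's value on the other day. If the set is one day's values, a participant with high exposure on both days could lose one of them although the Day 8/Day 1 contrast is unremarkable.

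**Working it through.** The documents give no false-flag rate, so there is no stated figure to reproduce first.

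**Inputs from the documents.** Protocol Synopsis: "Up to 40 participants will be enrolled to ensure that at least 30 evaluable participants complete", so n is 30 to 40. The multiplier is 3 (step 2c). SAP 9.1 names AUC and Cmax as log-normal, so a clean dataset is normal on the log scale.

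**Inputs assumed.** Between-participant log-SD 0.3 to 0.6 and within-participant log-SD 0.2 to 0.3. These imply a Day 1/Day 8 correlation from 0.09/(0.09+0.09) = 0.5 to 0.36/(0.36+0.04) = 0.9.

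**1. Flag rate of the rule.** For clean data, (value − mean of the rest) / (SD of the rest × √(1+1/(n−1))) follows t with n−2 degrees of freedom. The chance that one given value is flagged is p = 2 × P(t > 3/√(1+1/(n−1))). The chance for the dataset is at most n × p. Simulation of steps 2b to 2e gives the actual rate.

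| n | 3/√(1+1/(n−1)) | p | n × p | simulated |
|---|---|---|---|---|
| 6 | 2.739 | 0.0520 | 31% | 31% |
| 20 | 2.924 | 0.0091 | 18% | 18% |
| 30 | 2.950 | 0.00636 | 19% | 19% |
| 40 | 2.962 | 0.00524 | 21% | 20% |

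Iteration does not change the chance of at least one flag, because the first pass decides it. For comparison, a 3-SD limit with the suspect value kept in the mean and SD flags 3.3% of clean datasets of 30. Leaving the value out is what drives the rate.

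**2. If the test is run on each day's values** (n=30, total CV 50%, rule applied to both days for one parameter):

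| Day 1/Day 8 correlation | flag on either day | pair broken, given a flag | median shift, complete pairs | median shift, unpaired daily means |
|---|---|---|---|---|
| 0 | 34% | 99.9% | 4.7% | 4.6% |
| 0.5 | 32% | 97% | 2.4% | 4.6% |
| 0.7 | 32% | 92% | 1.6% | 4.5% |
| 0.9 | 28% | 76% | 0.7% | 4.1% |

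At correlation 0.7, CVs of 30% to 80% give 1.0% to 2.4% with complete pairs and 2.8% to 6.8% with unpaired means. Under the assumed log-SDs the medians are about 1–2% and 3–6%. The average signed shift is about zero. Coverage of a 90% CI from complete pairs falls by 1 to 2 points at most (for example 89.9% to 89.4% at correlation 0.7).

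**3. A calibrated multiplier.** For an overall 5% per dataset, k = t with n−2 df at 1−0.05/(2n), times √(1+1/(n−1)):

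- n=6: 4.851 × 1.0954 = 5.31
- n=20: 3.510 × 1.0260 = 3.60
- n=30: 3.479 × 1.0171 = 3.54
- n=40: 3.487 × 1.0127 = 3.53

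Simulated false-flag rates with these values are about 5% at each n.

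**4. Testing within-participant log differences instead.** With the fixed 3, this still flags 18% to 19% of clean datasets of 30. It also removes between-participant variance, so a participant with a truly large interaction stands out more. As an illustration, suppose 10% of participants have a Day 8/Day 1 ratio 3.5 times that of the others, with between/within log-SDs 0.6/0.2. The calibrated multiplier then removes 23% of them when applied to differences and 3% when applied by day. The current rule by day removes 9%.

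**The case against.** The strongest reply is that flagged does not mean dropped. The preamble makes both the test and the exclusion discretionary, and the test starts from a value already thought atypical. This stands. The 19% applies if the most extreme value of a dataset is tested; it does not predict that 19% of analyses lose valid data. The reply does not rescue the multiplier, because the procedure exists to justify exclusion and step 2e is worded as mandatory.

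A reader might also infer that the test is applied to each day separately and so breaks pairs as a matter of course. The SAP does not say so. Its comparison set could be one day's values, all values pooled, or within-participant differences. The figures by day are conditional on the first reading.

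A reader might further infer that the dabigatran ratio is biased. Clean data do not support this: the shift has no average direction and coverage hardly changes. Whether the complete-pairs or the unpaired figure applies depends on the statistical model, which is redacted. Protocol 9.1 also describes the analyses as not confirmatory. These points limit the size of the concern but do not remove it.

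**Conclusion.** The concern holds as a calibration fault. When run on clean log-normal data, the rule makes a valid value eligible for exclusion in about 19% of datasets of 30, 20% at n=40 and 31% at n=6. These rates need only the written rule, the planned n and the SAP's own log-normal description.

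The consequences for dabigatran are conditional and modest. If the test is run by day, about 28% to 34% of clean trials have a flag for a given parameter, for correlations from 0.9 down to 0, and most of these break a pair. The typical movement in the ratio is about 1–2% with complete pairs or 3–6% with unpaired daily means, under assumed variances. The documents do not support a claim that valid data will be lost at the 19% rate, or that the ratio is systematically biased. The fault is worth correcting because the correction is cheap.

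**What to change.** In SAP 9.3.1 step 2c, replace the fixed 3 with t with n−2 df at 1−0.05/(2n), times √(1+1/(n−1)), recomputed at each iteration.

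For dabigatran Cmax and AUC(0-∞), keep the analysis with all values and report results with and without any exclusion when n is 6 or more, as the SAP already does below 6. State which values form the comparison set, and reconcile step 2e with the preamble.

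Do not move the test to Day 8 minus Day 1 log differences. That avoids broken pairs, but it can raise the removal of participants with a truly large interaction, as step 4 of the working shows.

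The cost is SAP wording, a few lines of code and one extra sensitivity table. At the planned n, values between 3 and about 3.5 SD would stay in, so some confidence intervals would be slightly wider.
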